The CO2 study will assess the neuroprotective effect of CDI versus placebo (medical air insufflation) in addition to standard de-airing in patients undergoing left side heart valve surgery. In addition, the CO2 study will investigate the relationship between cerebral air embolic load and peri-operative brain injury detected by MRI and the relationship between perioperative brain injury and post-operative neurocognitive function.

4. Aims and objectives

The CO2 study aims to evaluate the efficacy and safety of CDI in patients undergoing planned open left side heart valve surgery.

It is hypothesised that in patients undergoing open heart valve surgery via partial or full sternotomy or thoracotomy, CDI plus standard de-airing is protective against ischaemic brain injury caused by cerebral embolisation (air microemboli) compared with medical air insufflation (placebo) plus standard de-airing.

Specific objectives of the trial are to evaluate:

- 1. The difference between groups receiving CDI or medical air insufflation in the incidence of acute clinical or radiographic ischemic brain injury between 2 and 10 days post procedure (primary outcome)
- The difference between groups receiving CDI or medical air insufflation with respect to a range of secondary outcomes (clinical, DWI lesion characteristics, adverse events, and patient-reported)
- The association between the burden and location with new ischemic brain lesions detected with DWI and post-operative neurocognitive function assessed by standard neurocognitive function tests

A mechanistic sub-study will also be conducted. Specific objectives of the mechanistic substudy are to determine whether there is a relationship between:

- 1. Intraoperative air embolic load detected by TCD
- 2. Cerebral blood flow (CBF) detected by TCD
- 3. Tissue oxygen index (TOI) of the frontal lobes by Near Infrared Spectroscopy (NIRS)

and ischaemic brain injury detected by MRI, and whether these relationships differ between the CDI and medical air insufflation groups.

5. Primary and secondary outcomes

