6.7 Unblinding

Requests to unblind on clinical grounds, e.g. to treat a complication, are not anticipated. However, if unblinding is requested during surgery on safety grounds, this will be facilitated by the Perfusionist. Any such request will be fully documented including who requested the unblinding and the reason for unblinding.

Requests to unblind after leaving the operating theatre should not occur; given that the effect of CDI/medical air insufflation is strictly limited to the period of delivery in the operating room. Therefore, the management of any subsequent SAE would not be altered by knowledge of the allocation. Unblinding rates will be monitored throughout the trial by the study team and by the independent Data Monitoring and Safety Committee (DMSC) that will be established to oversee participant safety in the trial (see Section 11 for further details).

Participants will be made aware before entering the study that they will not be told which treatment they will receive until after the trial has completed.

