6.8 Research procedures

Participants will be required to do, or undergo, the following tasks or investigations specifically for the study which are also outlined in table 1.

Pre-surgery:

- Read the CO2 study PIL (can be sent to the patient's home before the patient attends the hospital for their surgery)
- Provide informed consent to participate, if willing to do so
- Assessment of NIHSS, CAM, functional status (Barthel Index) and neurocognitive function (ACE III and TMT A&B)
 Complete quality of life questionnaire (SF-12)

During surgery:

- Receive the intervention allocated at randomisation during open heart valve surgery
- If participating in the mechanistic sub-study (Bristol centre only), a transcranial doppler ultrasound of the middle cerebral artery and near infrared spectroscopy of the frontal lobe will be conducted during surgery
- Assessment and reporting of any AEs and SAEs experienced

Post-surgery inpatient stay:

- Day 3 (between 3-5 days post-surgery): Assessment of NIHSS and CAM
- DW MRI brain scan ideally between 2 and 7, but no more than 10, days after surgery before hospital discharge
- Assessment and reporting of any AEs and SAEs experienced

Post-discharge:

Three months post-surgery (conducted remotely): Assessment of NIHSS, CAM, functional status (Barthel Index) and neurocognitive function (ACE III and TMT A&B) Complete quality of life questionnaire (SF-12).

Collection and assessment of any SAEs experienced after discharge from hospital

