7.1.1 Dosing schedule

Insufflation, with either carbon dioxide or medical air, will be initiated at a flow rate of 5 litres per minute (5.0L/min) before cannulation for cardiopulmonary bypass (CPB) and continued until 10 minutes post-CPB.

The allocated gas will be insufflated into the cardiothoracic wound through a gas diffuser that provides an almost 100% carbon dioxide / medical air atmosphere in the wound, as per the centre's local procedure.

The diffuser will be placed in the inferior part of the surgical incision.

When applied, the cardiotomy suction will be limited to a maximum rate of 1.5 L/min and the rough suction will be set to 10 L/min to avoid affecting the carbon dioxide/air concentrations in the field.

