7.2 Duration of treatment period

The duration of the treatment commences when the patient enters the operating room and concludes when the patient leaves the operating room after their surgery.

The duration of the procedure is expected to be between 2 hours and 4 hours.

Table 1 Schedule of assessments

			Post-surgery				
	Baseline	Intraoperative	Day 3 (between 3-5 days post op)	Day 2 – 7 (but no more than 10 days)	Discharge	Routine post-op follow-up	Three- month follow up
National Institutes of Health Stroke Scale	✓		✓				✓
Confusion Assessment Method	✓		✓				✓
Functional status: Barthel Index score	✓						✓
Neurocognitive function tests: Addenbrookes Cognitive Examination III and oral Trail Making Tests A&B	✓						√
Quality of life questionnaire (SF-12)	✓						✓
Assessment of post-operative complications					✓		
DW MRI brain				✓			
Assessment of serious adverse events (from randomisation to three month follow up), including readmissions			√	√	√	√	✓
Assessment of blinding success							✓
Transcranial doppler ultrasound*		√					
Near-infrared spectroscopy*		✓					

^{*100} patients at the Bristol centre only

8. Data collection

Each patient will be assigned a unique study number. All data recorded on paper relating to the participant will be located in CRF folders, which will be stored securely. Staff with authorisation to make changes to the study records, including the study database, will be listed on the study delegation log maintained at each centre.

Screening data will be collected for all patients undergoing open heart valve surgery considered for the study. Age, sex and Index of Multiple Deprivation (IMD) will be collected for all patients irrespective if they decline to participate. This information is collected to assess any difference in the patients that do not take part compared to patients that do, to establish if there are any socioeconomic barriers to participation.

Baseline data will be collected after consent. Consenting patients will be contacted by an authorised member of the local research team (as specified in the delegation log) who will provide the opportunity to understand the nature, significance, implications and risks of the trial so that they may make an informed decision if they should take part. If the patient decides to take part the member of the local research team will obtain informed consent.

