9.3 Period for recording adverse events

Data on adverse events will only be collected for the period of the participant's post-operative hospital stay.

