9.4 Period for recording serious adverse events

Data will be collected on all SAEs that occur from randomisation until the three-month follow up visit using the relevant CRFs.

Centres should expedite reporting of all fatal and 'unexpected' non-fatal SAEs that occur between randomisation and discharge to BTC CTEU within 24 hours of becoming aware, using an SAE report form.

The BTC CTEU will report all fatal and 'unexpected' non-fatal SAEs to the Sponsor. Unexpected events are those not listed in the trial protocol or on the CRFs. The Sponsor will report SUSARs to the MHRA and copy all reports to the BTC CTEU. BTC CTEU will report SUSARS to the REC.

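### Sections 6.8, 8(g) and 9.3 give three different adverse-event recording windows; read literally, 9.3 omits non-serious events that begin and resolve in theatre while the gas is given

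*Protocol*

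**What the plan says.** The protocol sets the recording period for adverse events in several places.

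- **Section 9.3:** "Data on adverse events will only be collected for the period of the participant's post-operative hospital stay".
- **Section 6.8:** under the heading for surgery it lists "Assessment and reporting of any AEs and SAEs experienced". The same line appears again under the post-surgery inpatient stay. After discharge, 6.8 lists SAEs only.
- **Section 8, item g:** adverse events are among the data collected at three months.
- **Section 9.4 (serious events):** "Data will be collected on all SAEs that occur from randomisation until the three-month follow up visit using the relevant CRFs".
- **Table 1:** the SAE row is labelled "Assessment of serious adverse events (from randomisation to three month follow up), including readmissions". There is no row for adverse events in general.

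Insufflation runs from "before cannulation for cardiopulmonary bypass (CPB) and continued until 10 minutes post-CPB" (section 7.1.1). Section 7.2 defines the treatment period as the time in the operating room: "The duration of the treatment commences when the patient enters the operating room and concludes when the patient leaves the operating room after their surgery".

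**The concern.** Sections 6.8 and 9.3 cannot both be followed. One makes adverse-event reporting a task during surgery; the other confines it to a period that begins after surgery. Item g of section 8 disagrees with 9.3 at the other end of the window.

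The start of the window matters more, because the intervention is confined to theatre. Section 6.7 says that "the effect of CDI/medical air insufflation is strictly limited to the period of delivery in the operating room". Section 4 sets out to evaluate safety as well as efficacy, and its second objective compares the groups on "secondary outcomes (clinical, DWI lesion characteristics, adverse events, and patient-reported". Section 2.3 reports the view that CDI may cause harm and says that it induces systemic hypercapnic acidosis. Section 13.2 says that risks are to be quantified by this study. A rule that begins recording non-serious events once the exposure has ended sits badly with those statements.

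An analysis plan cannot repair this, because the recording window decides which data exist. If some sites work from 6.8 and others from 9.3, the event counts will also differ between sites for reasons unrelated to the patients.

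**Working it through.** No alpha, power, rate or sample size is involved, and the protocol gives no figure to reproduce. The check is a comparison of windows.

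**Step 1: exposure.** Gas delivery starts before cannulation and stops 10 minutes after CPB (7.1.1). That lies inside the treatment period, which ends when the patient leaves the operating room (7.2).

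**Step 2: recording windows.**

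| Source | Events | Start | End | Covers theatre? |
|---|---|---|---|---|
| 6.8 | AEs and SAEs | Surgery | End of inpatient stay (SAEs only after discharge) | Yes |
| 8(g) | Adverse events | Not stated | Three months | Not stated |
| 9.3 | AEs | Post-operative stay | End of that stay | No |
| 9.4 | SAEs | Randomisation | Three-month visit | Yes |

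**Step 3: can the post-operative stay be read to include the operation?** Hardly. Section 6.8 puts surgery and the post-surgery inpatient stay under separate headings, and section 10.1 names the operation and the post-operative stay as distinct times for completing CRFs.

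**Step 4: which theatre events fall outside every window if 9.3 governs?**

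- Serious event in theatre: recorded under 9.4. The seriousness criteria in 9.2 are broad. Item g takes in events that may jeopardise the patient or need intervention to prevent a serious outcome.
- Non-serious event that starts in theatre and continues into the post-operative stay, such as an arrhythmia or inotrope use that persists: recorded under 9.3.
- Non-serious event that starts and resolves in theatre: outside 9.3 and 9.4. Only 6.8 provides for it.

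**Step 5: does Table 1 settle the matter?** No. It has no row for non-serious events. As the table reads here, the SAE row has blank cells at Baseline and Intraoperative followed by five ticks, although its label starts the period at randomisation. The Intraoperative column is ticked only for transcranial Doppler and near-infrared spectroscopy. The missing SAE tick is a separate slip in the schedule, and 9.4 still governs.

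**Step 6: item g of section 8.** It may be loose wording for SAEs, since 6.8 asks only for SAEs after discharge. As written, it still conflicts with 9.3.

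**The case against.** The case that this is only a matter of wording has substance.

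- The restriction in 9.3 can be read as a contrast with the three-month SAE window in 9.4, meant to end recording at discharge rather than to exclude theatre. Table 2 supports this. It lists as anticipated events some that by nature happen in theatre, such as conversion from minimal access and surgical damage.
- Data relating to surgery are collected (section 8, item e), and CRFs are completed during the operation (10.1). The CRFs and study manual, which decide what is captured in practice, are not shown.
- The outcome list in 5.1.2 names SAEs to three months, not all adverse events. No listed outcome therefore loses its exposure period.
- Randomisation is stratified by centre (6.5), so differing site practice should not by itself favour one arm.

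These points limit the consequence, but the conflict stands: no passage says which section prevails, and none outside 6.8 provides for recording non-serious events in theatre.

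A reader might infer something stronger: that the safety data for the whole exposure period are lost, because none of the gas-delivery time lies inside the 9.3 window. The protocol does not support that. Lack of overlap between two time windows does not measure events missed. Serious events and continuing events are captured by other rules. The statement in 6.7 concerns whether later unblinding would help in managing an SAE; it does not say that harm can show itself only in theatre. Harm from additional microemboli, which section 2.3 raises, would be looked for after surgery by MRI, NIHSS and CAM. Nor can Table 1 be cited as following 9.3, since it has no adverse-event row.

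**Conclusion.** The contradiction between 6.8 and 9.3 is real and unresolved, and 8(g) adds a second one. If 9.3 is followed as written, non-serious events that begin and end in theatre go unrecorded in either arm, for any of the 704 participants who have one. The protocol gives no rate for such events, so the number cannot be estimated. The other effect is possible inconsistency in recording between sites, which would add noise to event totals rather than bias the comparison.

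This rests on two assumptions: that 9.3 is applied literally, and that the surgery CRF does not already ask for such events. If the CRF does ask for them, the fault is confined to the text. The primary outcome and the listed SAE outcome are unaffected. The correction is still worth making, because the trial undertakes to evaluate safety and the rule as written omits part of the record from the period when the gas is given.

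**What to change.** Reconcile 6.8, 8(g), 9.3 and Table 1 to one stated adverse-event window that includes surgery, as 6.8 already requires. One option is randomisation, as for SAEs, to hospital discharge. Make clear in 8(g) whether the three-month item means SAEs only. Add an adverse-event row to Table 1 and tick the Intraoperative column for both adverse events and SAEs.

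Take intraoperative events from the hospital notes, which 10.1 names as the primary data source, onto the existing surgery CRF. Section 6.6 keeps the research nurses out of theatre and leaves the perfusionist unblinded, so causality should be assessed by blinded staff rather than by the perfusionist. Reporting intraoperative and post-operative events separately by arm would be useful but is optional.

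The cost is a short text amendment, slightly more CRF work and some additional causality review, since 9.2 requires that for every adverse event. No visit or test is added.

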9.4 Period for recording serious adverse events

Data will be collected on all SAEs that occur from randomisation until the three-month follow up visit using the relevant CRFs.

Centres should expedite reporting of all fatal and 'unexpected' non-fatal SAEs that occur between randomisation and discharge to BTC CTEU within 24 hours of becoming aware, using an SAE report form.

The BTC CTEU will report all fatal and 'unexpected' non-fatal SAEs to the Sponsor. Unexpected events are those not listed in the trial protocol or on the CRFs. The Sponsor will report SUSARs to the MHRA and copy all reports to the BTC CTEU. BTC CTEU will report SUSARS to the REC.

9.5 Expected adverse event association with trial intervention

There are no known expected adverse events from the trial intervention in this trial population. Any SAEs deemed related to the trial intervention are considered to be SUSARs and must be reported as per Figure 2.

9.6 Anticipated adverse events associated with surgery

In cardiac surgery, post-operative transient complications are expected and can be frequent. These are classified as 'anticipated adverse events of surgery'.

The AEs 'anticipated' in patients undergoing cardiac surgery are listed in Table 2.

Table 2 Anticipated adverse events of surgery

Body system	Anticipated adverse event						
	Myocardial Infarction						
	Cardiac arrest, requiring:						
	Resuscitation involving ventricular defibrillation / direct current (DC) shock						
	Chest reopening						
	External/internal cardiac massage						
Cardiovascular	Haemodynamic support, including use of:						
	Any inotropes						
	Intra-aortic balloon pump (IABP)						
	Pulmonary artery catheter						
	Vasodilator						
	Arrhythmias, including:						

Body system	Anticipated adverse event						
	Supraventricular tachycardia / atrial fibrillation / atrial flutter						
	Ventricular tachycardia						
	Requirement for pacing						
	Requirement for implantable cardioverter defibrillator (ICD)						
	Chest pain						
	Bleeding (needing re-operation or not)						
	Deep vein thrombosis (DVT)						
	Pulmonary embolus (PE)						
	Pericardial effusion / tamponade						
	Congestive heart failure requiring treatment						
	Pericarditis requiring treatment						
	Blood clots						
	Haematoma						
	Peripheral thrombophlebitis						
Blood & lymphatic							
disorders	Thrombocytopenia						
	Intubation / re-intubation and ventilation						
	Respiratory depression						
	Pneumonia						
	Dyspnoea						
	Cough						
	Intra-thoracic collection/abscess (requiring drainage or not)						
	Acute respiratory failure						
	Tracheostomy						
	Initiation of mask continuous positive airway pressure (CPAP) or non-invasive						
	ventilation						
Pulmonary	Acute respiratory distress syndrome (ARDS)						
•	Pneumothorax						
	Pleural effusion						
	Requirement for high flow oxygen						
	Atelectasis / pulmonary collapse						
	Surgical emphysema requiring intervention						
	Bronchopleural fistula						
	Prolonged air leak						
	Chylothorax						
	Acute aspiration						
	Tracheobronchial injury						
	New haemofiltration / dialysis						
Renal / Urology	Acute kidney injury						
Tional / Orology	Urinary retention requiring reinsertion of urinary catheter, delaying discharge, or						
	discharge with urinary catheter						
	Incontinence						
	Sepsis						
Infactive	Wound infection						
Infective	Respiratory infection						
	Mediastinitis						

Body system	Anticipated adverse event						
	Urinary Tract Infection (UTI)						
	Central venous catheter infection requiring removal or antibiotics						
	Unspecified infection						
	Other infections requiring antibiotics						
	Peptic ulcer / GI bleed /						
	Diagnostic laparotomy / laparoscopy						
	Ischaemic bowel requiring treatment						
	Pancreatitis						
	Vomiting						
	Nausea						
	Diarrhoea						
	Abdominal pain						
Control to ational (CI)	Dyspepsia						
Gastrointestinal (GI)	Constipation						
	Dry mouth or throat						
	Flatulence						
	Intestinal ischaemia						
	Delayed gastric emptying requiring intervention or delaying discharge or requiring maintenance of nasogastric drainage >7 days post-operatively						
	Dysphagia						
	New onset diabetes						
Hepatobiliary disorders	Hepatitis						
Ticpatobilially disorders	Jaundice						
	Anorexia						
Metabolism and nutrition	Increased appetite						
disorders	Hyperglycaemia						
	Hypoglycaemia						
	Hyponatraemia						
	Acute delirium (including hostility, confusion and emotional lability, depression,						
	anxiety, nervousness, thinking abnormal)						
	Agitation						
	Hallucinations						
	Somnolence						
	Dizziness						
No	Insomnia						
Neurological / Psychiatric	Mental impairment						
	Permanent stroke						
	Transient ischaemic attack (TIA)						
	Fitting/seizure						
	Recurrent laryngeal nerve damage						
	Acute psychosis						
	Delirium tremens						
	Other neurological injury						

Body system	Anticipated adverse event						
Eye disorders	Visual disturbances such as amblyopia, diplopia						
	Arthralgia						
Musculoskeletal	Myalgia						
Musculoskeletai	Back pain						
	Twitching						
General disorders &	Fatigue						
administration site	Fever						
conditions	Peripheral oedema						
Conditions	Generalised oedema						
	Pain						
	Elevated liver function tests:						
Investigations	 Aspartate aminotransferase (AST) 						
mvootigationo	 Alanine aminotransferase (ALT) 						
	Bilirubin						
	Weight gain						
Re-operation	Re-operation due to any cause						
	Incisional hernia						
	Acute diaphragmatic hernia						
	Bronchoscopy for any cause						
	Wound dehiscence						
Injury, poisoning,	Conversion from minimal access surgery to open surgery, for any reason						
procedural complication	Recurrent laryngeal nerve damage						
	Genital/renal tract injury						
	Bronchoscopy for any cause						
	Chyle leak / chylous ascites						
	Surgical complications, including anatomical/surgical damage (e.g. aortic rupture)						

10. Trial methods

To minimise bias, outcome measures are defined as far as possible on the basis of objective criteria. All personnel carrying out outcome assessments will be blinded; this will minimise detection and performance bias.

10.1 Source data

Clinical outcome data will be collected using purpose-designed case report forms (CRFs), which will be completed at baseline, during the participant's surgery and post-operative inpatient stay until discharge, routine post-operative follow-up appointment and the three-month post-surgery follow up (see Table 1 Fable 1 for schedule of data collection). The primary data source for these data will be the participant's hospital notes.

10.2 Planned recruitment rate

CDI can, in principle, be applied to most adults undergoing left side heart valve surgery. The 704 participants will be recruited over 24 months from at least eight high-volume UK NHS cardiac centres. Potential participants will be identified prospectively from lists of patients having cardiac surgery. Research staff considered part of the clinical care team are permitted to access this information.

Based on an average of 250 procedures per year per centre (http://bluebook.scts.org/), we estimate that 70% of patients will be eligible and approached and that 30% of those approached will consent to take part which is in line with the average 35% consent rate achieved across five other adult cardiac surgery trials run in Bristol (n=3055 eligible patients, 1114 consented) that required similar participant involvement. This equates to projected recruitment rate of 35 patients/month when all centres are open to recruitment allowing for a staggered opening of the sites.

